**Secondary Objective: Formal Statistical Testing**

The primary analysis for the secondary objective on the superiority of spesolimab over placebo. Time to first GPP flare up to week 48 for **Speso SC High** and **Speso SC Medium** versus placebo will be tested using **EM-PM** approach, i.e., primary Estimand using the

primary censoring rule, and via the stratified log-rank test stratified by the factor of the systemic concomitant use of GPP medications at randomisation (yes or no), based on the **RS**.

The estimated hazard ratios based on the same stratified Cox regression model as for the primary objective will be displayed for active spesolimab treatment arm versus placebo. In the case of zero event in one/some of the arms by stratum, the stratified Cox regression model will be conducted using Firth's penalization ([21, 22, 23](#)). A hazard ratio of less than one favors spesolimab. The treatment comparison will be made regardless of the treatment adherence or early discontinuation up to Week 48.

Kaplan-Meier (KM) estimates of the survival/failure probabilities at 4-week intervals, as well as the median survival time will be provided by treatment arm. 10th and 25th survival time percentile will be provided as deemed necessary. KM estimates of the event probability does not take the stratification factor, use of systemic GPP medication at baseline, into account.

As more flare events are expected within the first 3 months after randomisation (per CTP Section 7.5), the KM estimates are shown at a 1-week interval for the first 12 weeks of observation. Confidence intervals will be based on two-sided  $\alpha=0.05$  using complementary log(-log) transformation (*confype=loglog*). A KM curve will also be provided by treatment.

*Sample SAS Code*

```
PROC LIFETEST DATA=adtte;  
  TIME aval*cnsr (list);  
  STRATA stratification / GROUP=treatment TEST=logrank;  
RUN;
```

The primary method for handling of missing data and censoring rules on the time to the first GPP flare is described in [Section 6.6.2](#).

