A formal statistical hypothesis test will first be performed, at an overall 1-sided alpha level of 0.025, on the primary endpoint of time to first GPP flare up to week 48. A stratified log-rank test will be implemented for each dose of BI 300 mg q4w (high dose) and BI 300 mg q12w (medium dose) versus placebo, with stratification by the factor, concomitant use of systemic GPP medication at randomization (yes or no), and multiplicity will be controlled by the truncated Hochberg procedure (using a truncation fraction of 0.5). Subsequently, formal testing of all other endpoints included in the testing hierarchy (i.e. the key secondary, and then the secondary endpoints) will be performed, if the test on the primary endpoint is successful for at least one of the two doses (high or medium dose) of BI 655130.

The analysis of the key secondary endpoint for the proportion of patients with the occurrence of at least one GPP flare up to week 48 will be conducted subsequent to the test on the primary endpoint using a Cochran-Mantel Haenszel test, stratified by the factor concomitant use of systemic GPP medication at randomization (yes or no), for each of BI 655130 high and medium doses versus placebo. A truncated Hochberg procedure will be used to control for multiplicity on the tests of the key secondary endpoint, at an overall 1-sided alpha level of

0.025, if both doses were statistically significant on the test of the primary endpoint. If only one (high or medium) dose of BI 655130 was statistically significant on the test of the primary endpoint, then the same dose will be tested on the key secondary endpoint with a 1-sided alpha of 0.00625 (see [Section 7.1](#) for further details). If neither dose is declared to be statistically significantly superior to placebo for the primary endpoint, then no further testing in the hierarchical sequence will be conducted. Subsequent tests on the secondary endpoints included in the testing strategy (i.e. the time to first worsening of PSS up to week 48, and then on the time to first worsening of DLQI up to week 48), as well as tests on the primary and key secondary endpoints for the lowest dose of BI 655130 150 mg q12w versus placebo, are described in detail in Section 7.1.

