The null and alternative hypothesis for each of the BI high and medium doses versus placebo on the primary endpoint, the time to first GPP flare up to week 48 (defined by an increase in GPPGA score by ≥ 2 from baseline and the pustular component of GPPGA ≥ 2), are:

(1) BI 655130 300 mg q4w vs. Placebo

$H_{0,11}$: Effect of BI 655130 300 mg q4w on prolonging the time to the first GPP flare up to week 48 \leq Placebo;

versus the alternative hypothesis

$H_{A,11}$: Effect of BI 655130 300 mg q4w on prolonging the time to the first GPP flare up to week 48 $>$ Placebo.

(2) BI 655130 300 mg q12w vs. Placebo

$H_{0,12}$: Effect of BI 655130 300 mg q12w on prolonging the time to the first GPP flare up to week 48 \leq Placebo;

versus the alternative hypothesis

$H_{A,12}$: Effect of BI 655130 300 mg q12w on prolonging the time to the first GPP flare up to week 48 $>$ Placebo.

Regarding the first family, to control the overall type I error rate at a one-sided $\alpha = 0.025$ for the comparison of both high and medium doses of BI 655130 vs. Placebo on the primary endpoint, the truncated Hochberg method will be applied. The weight of the truncated Hochberg method is chosen as 0.5. If both primary endpoint p-values are ≤ 0.01875 (one-sided), then both comparisons involving the two BI 655130 dose regimens will be declared to be statistically significant. If the maximum of the p-values for the two dose comparisons is >0.01875 (one-sided), then the remaining p-value will be tested at the 0.0125 (one-sided level) and declared to be statistically significant only if that p-value is ≤ 0.0125 (one-sided).

The remaining alpha to be used in the second family will be 0.025 (one-sided) if both high and medium doses of BI 655130 are statistically significantly superior to Placebo on the primary endpoint. If only one comparison is successful then alpha will be $0.025/4=0.00625$ according to the truncated Hochberg procedure with a weight of 0.5. If neither dose is declared to be statistically significantly superior to Placebo for the primary endpoint, then no further formal testing in the hierarchical sequence will be conducted.

Second family: Test of the Key Secondary Endpoint

Further hypotheses will be tested on the key secondary endpoint in a hierarchical manner if the test for at least one dose of BI 655130 on the first family is successful.

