#### **Primary Objective: Dose Finding**

The Multiple Comparison Procedures and Modeling (MCP-Mod) approach ([19](#), [20](#)) is implemented in two main steps: (1) trial design stage; (2) trial analysis stage. The procedures for the trial design stage, including the selection of candidate models covering a suitable range of dose-response shapes and sample size and power calculations, are provided in the CTP Section 7.2.2. The procedures for the trial analysis stage are specified below.

For the primary analysis, the dose-response relationship will be modeled using the total planned dose. In this trial, the total is the sum of all planned randomized maintenance doses administered to the subject prior to week 48, including both loading and maintenance phase. Therefore, it is assumed that the cumulative concentration over time (AUC) and thus the cumulative total dose is the key driver of the efficacy response in the modeling part of MCP-Mod. [Table 7.4:1](#) shows the calculated total doses per treatment arm.

Table 7.4:1 Total dose per treatment arm during randomized maintenance treatment period

Treatment arm	Total dose
Speso SC Low: 300 mg day 1 150mg q12w	300mg at Day 1, 150mg at week 12, week 24 and week 36, Total dose:750 mg spesolimab
Speso SC Medium: 600 mg day 1 300mg q12w	600mg at Day 1, 300mg at week 12, week 24 and week 36, Total dose:1500 mg spesolimab
Speso SC High: 600 mg day 1 300mg q4w	600mg at Day 1, 300mg at week 4, week 8, week 12, week 36, week 20, week 24, week 28, w32, w36, week 40, week 44 Total dose: 3900 mg spesolimab
Placebo	Placebo at Day 1, week 4, week 8, week 12, week 16, week 20, week 24, week 28, w32, w36, week 40, week 44, Total dose 0 mg spesolimab

The responses for treatment difference estimate over placebo for each active dose group, which is based on the log hazard ratio of the active doses versus placebo, as well as their estimated variance-covariance matrix estimate for the primary endpoint are estimated by stratified Cox regression model on the time to the first GPP flare. The subsequent MCP-Mod analysis are based on the log hazard ratio from the stratified Cox regression model. In the case

of zero event in one/some of the arms by stratum, the stratified Cox regression model will be conducted using Firth's penalization ([21](#), [22](#), [23](#))

*Sample code*

```
PROC PHREG DATA=adtte;  
CLASS treatment stratification (REF='placebo');  
MODEL aval*cnsr (list)=treatment/ TIES=BRESLOW FIRTH;  

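### The SAP's sample log-rank code tests all four arms at once, so it does not produce the two one-sided dose-versus-placebo p-values that the text plans

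*SAP*

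**What the plan says.** Protocol Section 7 plans one test per dose: "A stratified log-rank test will be implemented for each dose of BI 300 mg q4w (high dose"), and likewise for the medium dose, each against placebo and stratified by systemic GPP medication use. The first family is tested "at an overall 1-sided alpha level of 0.025, on the primary endpoint of time to first GPP flare up to week 48". Protocol 7.1 states directional hypotheses for each dose and fixes the decision rule: "The weight of the truncated Hochberg method is chosen as 0.5", and "If both primary endpoint p-values are ≤ 0.01875 (one-sided"), both doses are declared significant. Otherwise the smaller p-value is tested at 0.0125. Protocol 7.2.2 and the prose of SAP 7.4.1 (Secondary Objective) repeat the dose-versus-placebo comparison.

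The sample code under that prose is "PROC LIFETEST DATA=adtte" followed by "STRATA stratification / GROUP=treatment TEST=logrank". It has no subset, no BY statement and no pairwise request. The Cox sample code in the same section (Primary Objective) starts with "PROC PHREG DATA=adtte" and takes every active-versus-placebo hazard ratio from that dataset, so `adtte` holds four treatment levels. That Cox code also contains "CLASS treatment stratification (REF='placebo", which attaches the reference option to the stratification variable.

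**The concern.** The rule in Protocol 7.1 needs two one-sided p-values. The code gives one omnibus chi-square, which cannot be entered into that rule. A programmer therefore has to adapt it, and the published SAP text does not say which arms belong in the risk sets or how the one-sided p-value is obtained.

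There are two obvious adaptations: request pairwise contrasts from the same four-arm run, or subset to two arms and run the test twice. They give different p-values. In the joint fit, expected flares and their variance come from risk sets pooled over all four arms, so effective arms distort the comparison of an ineffective dose with placebo.

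These p-values open every later family in the hierarchy, and SAP 7.5.2 carries the same analysis to PSS and DLQI worsening. The choice should not be left until after unblinding.

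**Working it through.** **What the code returns.** Four groups within strata give 4 − 1 = 3 degrees of freedom and no direction.

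**Decision thresholds (Protocol 7.1).** With weight 0.5: 0.5 × 0.025 + 0.5 × 0.025/2 = 0.01875 for both doses, and 0.025/2 = 0.0125 for the smaller p-value alone. The documents' figures agree.

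**Inputs (Protocol 7.5).** 30 per arm and 48 weeks (11.04 months), with the rate changing at 3 months. Base monthly first-flare rates before/after 3 months are 17.1%/3.0% placebo, 5.1%/0.9% low, 2.6%/0.4% medium and 1.7%/0.3% high. The placebo rate is 11.4%/2.0% in BaseMinus and 24.4%/4.2% in BasePlus. The stratum split and dropout are not given. They are assumed here: 15/15 and 24/6 per arm for the main error rates, with dropout 0%, 10% and 20%.

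**Reproducing the plan.** Expected events per arm = 30 × [1 − exp(−(3r₁ + 8.04r₂))].
- Placebo: 3 × 0.171 + 8.04 × 0.03 = 0.754, giving 15.9 events (plan 16).
- Low, medium and high by the same formula: 6.0, 3.1 and 2.2 (plan 6, 3, 2).
- Total: 27.2 (plan 27).

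Simulated Base power for at least one dose with two-arm tests is 99.1%, or 98.7% with 20% dropout, against the stated 98.6%. BaseMinus gave 85.7–88.4% against 83.4%. The stated figures are tied to the dose-finding step, which was not simulated.

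**The two routes.** With arm 0 = placebo and arm k = the tested dose, summed over event times and strata:
- Two-arm: z = Σ(d_k − d·n_k/n) / √V, with d, n and V computed from placebo and dose k only.
- Four-arm: z = (U_k − U_0) / √(V_kk + V_00 − 2V_k0), with U and V from risk sets of all four arms.

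Both sets of p-values then go through truncated Hochberg.

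**Why they differ.** At the start, placebo and dose k hold half the patients at risk, so the joint fit expects half the flares there. If medium is ineffective under Base rates, expected flares are 15.9 + 6.0 + 15.9 + 2.2 = 40.0, and the two compared arms contribute 31.8/40.0 = 0.795. The joint variance is then too small. If low is also ineffective the share is 31.8/49.9 = 0.64, and under the global null it is 0.5, so the excess should shrink and then vanish. Its size needs simulation because risk sets change as arms deplete.

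**False rejection of an ineffective high or medium dose after truncated Hochberg.** Main rows use 60,000 runs per case.

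| Scenario | Four-arm fit | Two-arm tests |
|---|---|---|
| Base, medium ineffective | 3.45–3.57% | 1.9–2.0% |
| Base, high ineffective | 3.30–3.43% | 1.9% |
| BaseMinus, one dose ineffective | 3.5–3.7% | 1.8–2.0% |
| BasePlus, one dose ineffective | 2.8% | 2.0% |
| One tested dose and low both ineffective | 2.3–2.7% | – |
| High and medium both ineffective, low HR 0.3 | 2.8–3.1% | – |
| Global null | 2.3–2.5% | 2.4–2.5% |

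Repeat simulations of 12,000 to 20,000 runs gave 3.1–3.3% for the Base cases, hence an overall range of 3.1–3.6%. The simulation standard error is √(0.035 × 0.965/60,000) = 0.08 point in the main runs and about 0.16 point at 12,000 runs. Treating the monthly rates as probabilities instead of hazards gives 3.4% for both Base cases. At a nominal 0.025 per comparison, before Hochberg, the Base rates are 4.2–4.5% for the four-arm route and 2.5–2.7% for the two-arm route.

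**The case against.** The governing text is right. The protocol and the SAP prose both name pairwise tests, and an omnibus p-value cannot silently replace them because the Hochberg rule needs two values. The snippet is labelled as sample code. The CMH sample in SAP 7.5.1.1 is just as unrestricted although it requests a two-group risk difference, so the samples may be templates with the restriction left implicit. SAP 6.1 refers technical details to an ADS plan that is not available here. All of this stands, and it makes the point a conflict between code and text, not a wrong test in the plan.

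Three further limits stand. The error rate belongs to an adaptation that neither document requests. The Base scenarios are non-monotone in dose (for example, medium equal to placebo while low keeps HR 0.3), whereas every candidate shape in Protocol 7.2.2 is monotone; strong control must still cover such configurations. Pairwise testing also follows only after a significant MCPMod result. That gate was not simulated, so the rates are upper bounds.

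A reader might infer that error control is lost whenever one dose works and the other does not. The figures do not support that: with the low dose also ineffective, the rate is about 2.3–2.7%, close to the ceiling. A reader might also link the Cox reference slip to these rates. It concerns a different procedure, and the SAP prose already defines those hazard ratios as active versus placebo.

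What the objection does not answer is that the code must be changed to yield the planned p-values, and that one natural change exceeds 2.5% in several configurations.

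**Conclusion.** The concern holds as a mismatch between the SAP's sample code and the planned analysis. As printed, the code supplies neither confirmatory p-value. Two-arm tests keep an ineffective dose's rejection rate at about 2% and the familywise error under the global null at 2.4–2.5%. Pairwise contrasts from the four-arm fit give about 3.1–3.6% under Base rates with the other two doses working. This rests on the protocol's flare rates, 30 per arm, no MCPMod gate, and assumed stratum splits and dropout that have little effect.

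The documents do not support saying that the planned test itself runs above 2.5%. The matter is worth correcting because it affects the p-values that gate the whole hierarchy.

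**What to change.** In SAP 7.4.1, and by reference 7.5.2, run PROC LIFETEST twice: once restricted to Placebo plus Speso SC High and once to Placebo plus Speso SC Medium, each stratified by medication use with the log-rank test. State that risk sets contain only the two arms compared, and that the one-sided p-value comes from the signed statistic.

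As a separate minor correction in the Cox sample code, write `CLASS treatment (REF='Placebo')` and keep the stratification variable in the STRATA statement only.

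The cost is a few lines of SAP code and one or two sentences. Design and data are unchanged, and two-arm tests reproduce the planned Base power (99.1% against 98.6%).

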## 7.5 SECONDARY ENDPOINT(S)

### 7.5.1 Key secondary endpoint(s)

#### 7.5.1.1 Primary analysis of the key secondary endpoint(s)

The key secondary endpoint serves the secondary objective of the trial through formal statistical testing procedure.

The primary analysis for the key secondary endpoint will be tested using **EM-MI** approach, i.e., primary Estimand after applying multiple imputation. The stratified Cochran-Mantel-Haenszel (CMH) test based on the RS will be used. If a subject discontinues the treatment early but continues in the study, the primary analysis will include subjects' on- and off-treatment data up to Week 48.

The stratified Cochran-Mantel-Haenszel (CMH) test will be performed for each dose level of spesolimab versus placebo stratified by the concomitant use of systemic GPP medications at randomisation (yes or no) based on the RS. The difference in the proportion of subjects who have at least one GPP flare up to week 48, will be presented for each active group versus the placebo group using the Mantel-Haenszel type weighted average of risk differences. The averaged risk difference will use weights as proposed by Greenland & Robins (24). The associated confidence intervals of the averaged risk difference will use Sato's method (25).

[figure not shown]
*Sample code for CMH test*

```
PROC FREQ DATA=data;  
  TABLES stratification*treatment*response / CMH commonriskdiff nopercen  
  RISKDIFF(COMMON COLUMN=2);
```

RUN;

The primary method for handling of missing data on the occurrence of at least one GPP flare is described in [Section 6.6.2](#).

In addition to the risk difference up to week 48, as a monotone binary endpoint, the proportion of subjects who have at least one GPP flare for each arm up to certain time points may also be provided using data handled by **EM-MI** approach. The certain time points are specified as each visit at a 4-week interval up to week 48. 95% confidence interval (CI) of the proportion will be calculated using the method of Wilson.

### **7.5.2 Secondary endpoint(s)**

The secondary endpoints defined below, for the secondary objective of the trial only, are included into the statistical testing strategy.

*Time to first worsening of Psoriasis Symptom Scale (PSS) up to week 48 defined as a 4-point increase in total score from baseline. Intake of rescue medication, or investigator-prescribed SoC, will be considered as onset of a worsening.*

*Time to first worsening of Dermatology Quality of Life Index (DLQI) up to week 48 defined as a 4-point increase in total score from baseline. Intake of rescue medication, or investigator-prescribed SoC, will be considered as onset of a worsening.*

The primary analyses of the two secondary endpoints are as same as that of the primary endpoint using **EM-PM** approach based on RS.

[figure not shown]
[figure not shown]
Subjects with the following situation/s will be censored at Day 1 in all corresponding time-to-event analyses

[figure not shown]
- Without a baseline evaluation in PSS/DLQI
- Do not eligible for the evaluation of worsening
  - PSS baseline >12;
  - DLQI baseline >26;
  - DLQI questionnaire for subject whose age is under 16.

[figure not shown]
The below-defined secondary endpoint is not included into the statistical testing strategy of the secondary objective.

*Sustained remission, defined as a subject with a GPPGA score of 0 or 1 (clear or almost clear) at all visits up to week 48, without intake of rescue medication, or investigator-prescribed SoC.*

[figure not shown]
The primary analysis of the above secondary endpoints is consistent with that of the key secondary endpoint using **EM-MI** approach.

[figure not shown]

[figure not shown]
[figure not shown]

## **7.8 SAFETY ANALYSIS**

Safety analyses for randomized maintenance treatment period, flare treatment period and OL maintenance treatment period will be performed based on the SAF, SAF-FT and SAF-MT respectively following BI standards. Data will be summarized descriptively without any imputation based on data available of each corresponding treatment period. In addition, AEs post any spesolimab (i.v. or s.c.) will be summarized. No hypothesis testing is planned. Since the onset time of an AE will not be collected in the trial, any AE which occurs on the same day as the first dose of each treatment period will be assigned to that treatment period.

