Patients will be offered to enter into an open label extension (OLE) trial (1368-0025), if they have completed the treatment period in this study up to EoS1 (i.e. without premature discontinuation of trial treatment), agree to participate in the OLE trial and meet the eligibility criteria for the OLE trial.

Patients who do not qualify to enter into the open label extension (OLE) trial or who may have qualified, but do not agree to participate in the OLE trial, will be followed as described in [section 3.3.4.1](#) handling of patients with premature treatment discontinuation.

The primary analysis of this trial is planned to be performed once all randomized patients have completed or early discontinued from the 48 week treatment period; a database lock for the primary analysis will then be performed. Final analysis is planned to be performed at the end of the trial once all randomized patients have completed the trial (including any follow-up period) if applicable.

The primary analysis and final analysis may be performed as a single analysis (at the time of trial completion), if, prior to the time of the primary analysis, the trial team agrees that the expected time interval between the planned analyses is insufficient to justify the performance of separate analyses.

Handling of GPP Flares:

If a patient experiences the first GPP flare (increase in GPPGA score by ≥ 2 from baseline and the pustular component of GPPGA ≥ 2) during the randomized maintenance treatment period, a rescue treatment with i.v. open label dose of 900 mg BI 655130 should be administered (R1/D1). The investigators should encourage the patient to inform them at the first signs of onset of a GPP flare. If a patient suspects that they have a GPP flare in between the protocol specified scheduled visits, they should contact the investigator to determine whether to make an unscheduled visit and return to the clinic/site for assessment. After confirming the onset of a GPP flare requiring treatment and subsequently receiving the i.v. dose of BI 655130, the patients will be seen at R2/D4 and R3/D8 of week 1 (daily if hospitalized), week 2, week 3, week 4, and week 8 of the rescue treatment period (see [Flow Chart 2](#)). A patient may qualify to receive another rescue treatment with open label i.v. dose of 900 mg of BI 655130 at R3/D8, if either of the following criteria are met.

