5.2.6 Assessment of adverse events

5.2.6.1 Definitions of AEs

5.2.6.1.1 Adverse event

An AE is defined as any untoward medical occurrence in a patient or clinical investigation subject administered a medicinal product and which does not necessarily have to have a causal relationship with this treatment.

An AE can therefore be any unfavourable and unintended sign (including an abnormal laboratory finding), symptom, or disease temporally associated with the use of a medicinal product, whether or not considered related to the medicinal product.

The following should also be recorded as an AE in the CRF and BI SAE form (if applicable):

- Worsening of the underlying disease or of other pre-existing conditions.
- Changes in vital signs, ECG, physical examination and laboratory test results, if they are judged clinically relevant by the investigator.

If such abnormalities already exist prior to trial inclusion, they will be considered as baseline conditions and should be collected in the eCRF only.

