## 6. GENERAL ANALYSIS DEFINITIONS

### 6.1 TREATMENTS

For basic study information on the treatment to be administered, assignment to treatment, and selection of dose, refer to Section 3 and 4 of the CTP.

For the analysis of adverse event, the study phases are defined as in [Table 6.1:1](#).

Table 6.1: 1 Flow chart of analysis phases of the study

Study analysis phase	Description	Start (included)	End (included)
Screening phase	Screening	Earliest of (Date of informed consent, first screening procedure)	Date/time of start of the first randomized study treatment minus 1 minute
Randomized maintenance treatment phase	On randomized treatment period	Date/time of start of the first randomized study treatment (V2/D1)	Earliest of i) Date/time of start of the rescue treatment with i.v. spesolimab minus 1 minute. ii) Date of the end of last randomized study treatment + REP  (112 days) at 23:59. iii) Date/time of the first treatment in OLE trial 1368.25 if the subject is rolled over, iv) last contact date on End of Study page at 23:59 if subject is not rolled over.
Flare treatment phase (if applicable)	On flare treatment period	Date/time of start of the first rescue treatment with spesolimab i.v. 900 mg	Earliest of i) Date/time of start of the first OL maintenance treatment minus 1 minute. ii) Date of the end of last rescue treatment + REP  (112 days) at 23:59. iii) Date/time of the first treatment in OLE trial 1368.25 if the subject is rolled over, iv) last contact date on End of Study page at 23:59 if subject is not rolled over
OL maintenance phase (if applicable)	On OL maintenance treatment period	Date/time of start of the first OL maintenance treatment	Earliest of i) Date of the end of last OL maintenance treatment + REP  (112 days) at 23:59. ii) Date/time of the first treatment in OLE trial 1368.25 if the subject is rolled over, iii) last contact date on End of Study page at 23:59 if subject is not rolled over.
Off treatment phase 	Off-treatment period	Date of the end of last study treatment (including randomized treatment, flare treatment and OL maintenance treatment) + REP  (112 days) + 1 day at 0:00	i) Date/time of the first treatment in OLE trial 1368.25 if subject is rolled over, ii) last contact date on End of Study page at 23:59 if subject is not rolled over.

Dates are defined individually per subject. An analysis phase will not extend beyond the start date of the following phase.

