### **7.8.1 Adverse Events**

AEs will be coded with the most recent version of MedDRA. Subjects will be analyzed according to the actual treatment received in each treatment period, i.e., randomized maintenance period, flare treatment period and OL maintenance period, respectively. In addition, the analysis for overall period post use of any spesolimab (s.c. or i.v.) will be performed for all subjects received at least one dose of spesolimab (s.c. or i.v.).

The exposure adjusted incidence rate (per 100 subject years) of a treatment emergent adverse event (TEAE) is defined as the number of subjects experiencing the adverse event per treatment group during time at risk divided by the total time of subjects at risk in that treatment group to contribute the event to the analysis multiplied by 100 (per 100 subject years), where:

Time at risk [subject years] = (date of onset of TEAE – the first dose of treatment in the applicable treatment period + 1) / 365.25 for subjects with onset of TEAE

During randomized maintenance treatment period, if the selected treatment emergent adverse event did not occur, the time at risk will be censored at the end of the treatment period as defined in [Section 6.1](#).

To distinguish the GPP flare symptoms from treatment emergent adverse event, sensitivity analysis for the safety during randomized maintenance treatment period will be done by censoring the time at risk to 7 days prior to first spesolimab iv treatment for subject who received the rescue spesolimab i.v. treatment. For subjects without the flare treatment, the time at risk will be censored at the end of the randomized treatment period as specified in [Section 6.1](#).

For the randomized maintenance treatment period, analysis of the time to the first specific AE, which will be pre-defined in the ISS SAP, may also be provided. Kaplan-Meier (KM) estimates of the survival/failure probabilities, as well as the median time-to-event, will be displayed by randomized treatment arm. Confidence intervals will be based on two-sided  $\alpha=0.05$  using complementary log(-log) transformation (conftype=loglog). A Kaplan-Meier curve will also be produced. For subjects who do not experience the defined the event, the time at risk will be censored at the end of the treatment period as defined in [Section 6.1](#).

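### The SAP's same-day rule counts a GPP flare dated on the first rescue day as treatment-emergent on i.v. spesolimab and removes it from the randomised-arm AE table

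*SAP*

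**What the plan says.** SAP Table 6.1: 1 cuts the AE phases to the minute. For a rescued patient the randomised phase ends at "Date/time of start of the rescue treatment with i.v. spesolimab minus 1 minute", and the flare-treatment phase begins at "Date/time of start of the first rescue treatment with spesolimab i.v. 900 mg". The note under the table adds: "An analysis phase will not extend beyond the start date of the following phase".

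AE onset is recorded to the day only, so SAP 7.8 settles ties by date: "any AE which occurs on the same day as the first dose of each treatment period will be assigned to that treatment period".

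The protocol fixes two further points. Section 5.2.6.1.1 lists among the things to be recorded as AEs: "Worsening of the underlying disease or of other pre-existing conditions". No exemption for GPP flares is visible. Section 3.1 gives the order of events that leads into the rescue visit schedule: "After confirming the onset of a GPP flare requiring treatment and subsequently receiving the i.v. dose of BI 655130".

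Protocol 7.2.5 says that, for patients given rescue spesolimab, safety findings occurring after that intake are left out of the displays by planned treatment and shown in the summaries after any spesolimab use.

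SAP 7.8.1 recognises that flare symptoms can be confused with AEs, but only for the randomised period, with a cut-off counted back from the first i.v. dose: "sensitivity analysis for the safety during randomized maintenance treatment period will be done by censoring the time at risk to 7 days prior".

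**The concern.** The tie rule is a sensible default when the order of dose and event is unknown. For the flare that led to rescue, the order is known from the design: the flare comes first and is the reason for the infusion. If its recorded onset date is the infusion date, the rule reverses that order. The i.v. table then shows the treated condition as an event that emerged on the drug, and the randomised arm loses an event that arose there.

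Two safety objectives in Protocol 2.1.1 depend on these tables: the multiple s.c. doses, and the i.v. dose in acute flare. The i.v. data also feed the interim analysis intended for an acute-flare submission (Protocol 7.2.7; SAP 3). Flares requiring hospitalisation are SAEs (Protocol 5.2.6.1.2), so the SAE tables are exposed in the same way. Most first flares are expected on placebo, so the randomised comparison would lose events mainly from that arm.

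**Working it through.** **Tracing one flare AE with onset date equal to R1/D1**

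1. It is an AE, because it is a worsening of the underlying disease (Protocol 5.2.6.1.1).
2. It began before the infusion, because confirmation precedes dosing (Protocol 3.1; Flow Chart 2 places F0 before R1).
3. With a known onset time, Table 6.1: 1 would put it in the randomised phase, which runs to one minute before the infusion.
4. Onset time is not collected, so the date rule in SAP 7.8 puts it in the flare-treatment phase.
5. Phases do not overlap, so it is absent from the randomised phase.
6. A correctly treated placebo patient has had no earlier spesolimab (exclusion criterion 4b), so the flare also enters the summaries after any spesolimab. For an active-arm patient it belongs in those summaries anyway, because the s.c. drug came first.

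**Comparison with neighbouring rules**

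- Protocol 7.2.5 moves only findings after rescue intake. The triggering flare is not one of them.
- SAP 6.7 treats a measurement with a date but no time, taken on a period's first dosing day, as pre-treatment. SAP 7.8 resolves the same ambiguity the opposite way for AEs.
- The 7-day analysis in SAP 7.8.1 shortens the randomised period. It does not return same-day flares to that period or remove them from the i.v. period.
- SAP 6.6.3 sets a missing R1/D1 date to the flare date, which can itself create a tie.

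**Scale: reproducing the plan's event count.** The inputs are 30 patients per arm and the base-scenario monthly rates in Protocol Table 7.5: 2, used as hazards h1 (first 3 months) and h2 (afterwards). T = 48 × 7 / 30.4375 = 11.04 months. Expected first flares = 30 × (1 − exp(−(3·h1 + (T − 3)·h2))).

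| Arm | h1 | h2 | Result | Plan |
|---|---|---|---|---|
| 300 mg q4w | 0.017 | 0.003 | 2.17 | 2 |
| 300 mg q12w | 0.026 | 0.004 | 3.13 | 3 |
| 150 mg q12w | 0.051 | 0.009 | 6.05 | 6 |
| Placebo | 0.171 | 0.030 | 15.89 | 16 |
| Total | | | 27.24 | 27 |

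**Scale: how many could move.** The documents do not give the share of flare AEs dated on the infusion day. The shares below are assumptions. They also take every first flare to be rescued and recorded as an AE.

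| Assumed same-day share | Moved to i.v. period (of 27) | Moved from placebo (of 16) | Left in placebo AE table |
|---|---|---|---|
| 25% | 6.75, about 7 | 4 | 12 |
| 50% | 13.5, about 14 | 8 | 8 |
| 100% | 27 | 16 | 0 |

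**Exposure-adjusted rate.** By the formula in SAP 7.8.1, a same-day flare contributes (0 + 1)/365.25 = 0.0027 years at risk in the i.v. period. As an illustration, take 7 of 27 patients affected, no other event of that term, and 84 days at risk for the other 20 (an assumption). The time at risk is (7 × 1 + 20 × 84)/365.25 = 4.62 years, and the rate is 100 × 7/4.62 = about 152 per 100 patient-years. This rate would describe the indication for the infusion.

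**The case against.** The strongest counter-argument is that the rule errs on the cautious side in an open-label, single-arm, descriptive table. Infusion reactions are AEs of special interest, onset time is not recorded, and a fever on the infusion day may come from the flare or from the drug. Moving everything that looks like a flare symptom out of the i.v. period could hide a reaction. This stands, and it limits the change to the flare AE itself.

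The number affected may be small. Patients who suspect a flare between visits contact the site, so onset will often predate the visit; F0 is a separate step; and pre-infusion laboratory samples may be taken a day earlier. Any flare AE dated before R1/D1 stays in the randomised period. This also stands: the table's last row is a ceiling, not an expectation.

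No safety hypothesis is tested, and a reader of the i.v. table knows that every patient there was treated for a flare. That reduces the harm in the i.v. table but does not restore the event to the randomised arm.

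Parts of the SAP safety section are redacted, and AE handling also relies on sponsor guides that are not available here. A correcting rule may exist there; none can be seen.

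**Conclusion.** The point holds for one event type. A GPP flare AE dated R1/D1 is counted as treatment-emergent on i.v. spesolimab and lost from the randomised-arm AE table, against the order fixed by the design and beyond what Protocol 7.2.5 moves. The size is unknown. The upper bound under the base scenario is about 27 flares, 16 of them on placebo, and it rests on every flare being rescued, recorded as an AE and dated on the infusion day.

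A reader might infer more than the documents support:

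- **The placebo AE table will lose all its flares.** This needs a 100% same-day share, which nothing in the documents supports.
- **The efficacy results are affected.** They are not. The flare still counts for the randomised arm in the primary and key secondary endpoints (SAP 5.1, 5.2.1).
- **Same-day flares should leave the Overall Speso tables for everyone.** Of the 27 expected flares, 2 + 3 + 6 = 11 are in patients who had already received s.c. spesolimab, and these belong there.
- **The tie rule is wrong in general.** For other same-day AEs the order is unknown, and the rule is reasonable.

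**What to change.** Add an exception to SAP 7.8:

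- The AE of GPP flare or worsening that led to rescue, with onset date equal to R1/D1, is assigned to the randomised period and is not counted as treatment-emergent in the flare-treatment period.
- It is excluded from the summaries after any spesolimab only for patients randomised to placebo with no prior spesolimab. For active-arm patients it stays in.
- All other AEs dated R1/D1, including fever and possible infusion reactions, remain under the present rule.
- Deterioration of the flare after the infusion remains treatment-emergent, in line with Protocol 7.2.5.
- The present rule, applied to all AEs, is shown as a sensitivity display.

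The cost is a short SAP addition and one extra display. No new eCRF item is needed. The downside is that the index-flare AE terms must be identified before unblinding. This could be done alongside the review of concomitant medication that SAP 7.2 already requires before database lock. For the open-label interim analysis only the flare-period part can be applied, because the randomised arm stays blinded at that point.
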